7.2.5. Vital Signs, Physical Examination, and ECGs

Patients will have a physical examination that includes major body systems and measurements of body weight, height, body temperature, sitting blood pressure, heart rate, respiratory rate, and PaO₂ (obtained either by arterial blood gas analyses or from saturation of oxygen (SpO₂) by pulse oximetry, and its respective FiO₂ ([Appendix 12 Imputation of FiO₂ from oxygen flow values. High-flow oxygen therapy](#)), at the timepoints specified in the Schedule of Assessments ([Appendix 5](#)). Additionally, height will be measured at screening. To estimate the PaO₂/FiO₂ ratio, the required equation would be used for imputing PaO₂ from SpO₂ ([Appendix 9 – Imputation of PaO₂ from SpO₂](#)), and the information on the oxygen delivery devices and oxygen flow prescribed would be utilised for imputation of FiO₂.

Triplet 12-lead (with a 10-second rhythm strip) tracings will be used for all ECGs, taken at the timepoints described in the Schedule of Assessments ([Appendix 5](#)). Preferably, the machine used has a capacity to automatically calculate the standard intervals. At each test point, QTcF prolongation to be assessed at screening (defined as the visit with less than 24 hours of difference before the first infusion of the study drug) and on Days 1, 3, and 31 (± 3 days). If the mean QTc is prolonged (>500 msec, ie, CTCAE Grade ≥ 3) or a change >30 msec from baseline is observed, then the ECGs should be re-evaluated by a specialist at the site for confirmation as soon as the finding is made, including verification that the machine reading is accurate. If manual reading verifies a QTc >500 msec, immediate correction for reversible causes (including electrolyte abnormalities, hypoxia and concomitant medication with drugs with the potential to prolong the QTc interval) should be performed.

Any QTcF values > 500 msec will be flagged as increasing the likelihood of the treatment being proarrhythmic (per ICH Guidance E14).

Each episode of prolongation of the QTc interval will be evaluated by a specialist to determine if it is due to the investigational product(s) or due to other potential precipitating factors (e.g., change in patient clinical condition, effect of concurrent medication, electrolyte disturbance).

If a patient experiences any cardiac or neurologic AEs (especially syncope, dizziness, seizures, or stroke), a 12-lead ECG in triplicate should be obtained at the time of the event.

Clinically significant new findings seen on any ECGs taken after screening should be recorded as AEs.

Additionally, a dedicated QTc substudy will be performed in a subset of approximately 50 patients with ECGs collected over Days 1 to 3 using Holter monitors to assess treatment impact on QTc prolongation. See [Appendix 8](#) for objectives and respective endpoints planned for the QTc substudy. The substudy patients will have blood sampling for pharmacokinetic assessments over Days 1 to 4.

7.3. Pharmacokinetic Analysis

Patients participating in the QTc substudy will have blood sampling for PK assessments over Days 1 to 4. See [Appendix 8 \(Protocol for QTc Substudy\)](#) for details.

7.4. Study Procedures

7.4.1. Prestudy Screening (Days 0 to 1)

Each candidate patient will be examined before starting the study to determine eligibility for participation. Screening assessments normally should be completed within 24 hours before the first administration of study medication. The following evaluations will be performed:

- Informed consent must be obtained before any study specific procedure.
- Verification of eligibility criteria.
- Demographics.
- Charlson Comorbidity Index.
- Medical history.
- Physical examination including body weight, height, vital signs (temperature, blood pressure, heart rate, respiratory rate), PaO₂ (obtained either by arterial blood gas analyses or from saturation of oxygen (SpO₂) by pulse oximetry, and its respective FiO₂ ([Appendix 9](#))).
- Clinical status using the 11-point WHO Clinical Progression Scale ([Appendix 13](#)).
- Functional status using the Barthel index ([Appendix 7](#)) score for the previous month before screening.
- Functional status using the Barthel index score at screening.
- Pregnancy test for females of child-bearing potential.
- Screening symptoms and complaints.
- Adverse events/TEAEs ([Appendix 1](#)).
- Concomitant medications.
- Haematology (RBC, haemoglobin, haematocrit, WBC with differential, platelet count) (tests performed within 24 hours of screening do not have to be repeated).
- Serum chemistry (ALT, AST, total bilirubin, sodium, potassium, calcium [albumin adjusted], magnesium, creatinine, calculated creatinine clearance [Cockcroft-Gault equation], CPK, and troponin [I or T according to local practice]) (test performed within the previous 24 hours before screening is accepted and does not have to be repeated).
- Qualitative PCR or antigen test for COVID-19 by local laboratory collected no more than 72 hours before study treatment on Day 1. Record SARS-CoV-2 variant, if available.
- Triplicate 12-lead ECG to assess QTcF interval.

- Screening registration in IWRS.

7.4.2. Evaluations During Study Treatment

7.4.2.1. Days 1 to 4

The following assessments will be completed on Days 1 to 4 unless otherwise stated:

- Randomisation in IWRS (*Day 1 only*).
- Vital signs (temperature, blood pressure, heart rate, respiratory rate) and PaO₂ (obtained either by arterial blood gas analyses or from saturation of oxygen (SpO₂) by pulse oximetry, and its respective FiO₂ just before the start and immediately at the end of the plitidepsin infusion (for patients randomised to plitidepsin arms) and once daily while hospitalised (all arms)).
- Physical examination.
- TriPLICATE 12-lead ECG to assess QTcF interval (*Days 1 and 3 postinfusion*).
- Chest imaging (CT scan or x-ray) (*Day 1 only*) (chest imaging performed within 48 hours of Day 1 is accepted and does not have to be repeated).
- Haematology (RBC, haemoglobin, haematocrit, WBC with differential, platelet count).
- Coagulation (D-dimer).
- Serum chemistry (ALT, AST, alkaline phosphatase, GGT, LDH, total bilirubin, direct bilirubin, glucose [fasting], sodium, potassium, calcium (albumin adjusted calculation), magnesium, BUN, creatinine, calculated creatinine clearance [Cockcroft-Gault equation], CPK, troponin T [high sensitivity; *Day 1 only*], NT-Pro-BNP [*Day 1 only*], albumin, amylase, lipase, and procalcitonin).
- Immunology (CRP, ferritin, IL-1 β , IL-6, IL-10, and TNF α).
- Quantitative PCR for COVID-19 viral load (*Day 1 only, prior to initiating study treatment*).
- Serological SARS-CoV-2 testing (IgG) (*Day 1 only*).
- Concomitant medications.
- Adverse events/TEAEs.
- Clinical status, using the 11-point WHO Clinical Progression Scale ([Appendix 13](#)).
- Administration of dexamethasone base 6.6 mg/day IV (equivalent to 8 mg dexamethasone phosphate) on Days 1 to 3 (administered as a premedication in plitidepsin arms), followed by 6 mg/day PO/IV (equivalent to 7.2 mg dexamethasone phosphate) from Day 4 and up to a total cumulative dose of 60 mg of dexamethasone base (per physician judgement based on patient clinical condition and evolution).
- Administration of plitidepsin on Days 1 to 3 (*patients randomised to plitidepsin arms*) Administration of plitidepsin will require at least 1.5 hours (± 5 mins): 30 minutes for administration of prophylactic medications for infusion reactions (which should be

ideally completed 20 to 30 minutes before plitidepsin infusion start and, exceptionally, up to 2 h pre-infusion of plitidepsin) followed by a 60-minute infusion of plitidepsin. A 30 (± 5) minute window is allowed for the plitidepsin administration between each day, and plitidepsin should not be given earlier than 23.5 hours on Days 2 and 3 of previous day plitidepsin administration.

- Administration of remdesivir 200 mg IV on Day 1, followed by 100 mg/day IV on Days 2 to 5 (*per physician decision for patients randomised to control arm*). Administration of favipiravir 1600 mg BID PO on Day 1, followed by 600 mg BID PO daily for 2 to 5 days (*per physician decision for patients randomised to control arm*). Administration of any other regulatory-approved antiviral treatment to follow approved SmPC.

7.4.2.2. Days 5, 6, and 7

The following assessments will be completed on Days 5, 6, and 7 (or until discharged) unless otherwise stated:

- Vital signs (temperature, blood pressure, heart rate, respiratory rate) and PaO₂ (obtained either by arterial blood gas analyses or from saturation of oxygen (SpO₂) by pulse oximetry, and its respective FiO₂ once daily while hospitalised).
- Concomitant medications.
- Adverse events/TEAEs.
- Clinical status, using the 11-point WHO Clinical Progression Scale (highest category that applies) ([Appendix 13](#)):

For patients who remain hospitalised after Day 7, the above assessments should be performed once each day until discharge.

Additionally, administration of dexamethasone base will be continued at 6 mg/day PO/IV (equivalent to 7.2 mg dexamethasone phosphate), per physician judgement based on patient clinical condition and evolution. Administration of remdesivir 100 mg/day IV or favipiravir 600 mg BID PO daily may continue until Day 5 per physician's decision for patients randomised to control arm. Administration of any other regulatory-approved antiviral treatment to follow approved SmPC.

7.4.2.3. Days 8 and 31

The following assessments will be performed on Days 8 (± 1 day), 31 (± 3 days), and study discontinuation unless otherwise stated:

- IWRS registration (*Day 31 and at end of study visit*).
- Vital signs (temperature, blood pressure, heart rate, respiratory rate) and PaO₂ (obtained either by arterial blood gas analyses or from saturation of oxygen (SpO₂) by pulse oximetry, and its respective FiO₂).
- Physical examination.
- TriPLICATE 12-lead ECG to assess QTcF interval (*Day 31 only and at end of study visit*).

- Haematology (RBC, haemoglobin, haematocrit, WBC with differential, platelet count).
- Coagulation (D-dimer).
- Serum chemistry (ALT, AST, alkaline phosphatase, GGT, LDH, total bilirubin, direct bilirubin, glucose [fasting], sodium, potassium, calcium (albumin adjusted calculation), magnesium, BUN, creatinine, calculated creatinine clearance [Cockcroft-Gault equation], CPK, troponin T [high sensitivity], NT-pro-BNP, albumin, amylase, lipase, and procalcitonin).
- Immunology (CRP, ferritin, IL-1 β , IL-6, IL-10, and TNF α).
- Quantitative PCR for COVID-19 viral load (*Day 8 only*).
- Serological SARS-CoV-2 testing (IgG) (*Day 31 only and at end of study visit*).
- Chest imaging (using same technique as baseline).
- Concomitant medications.
- Adverse events/TEAEs.
- Functional status using the Barthel index ([Appendix 7](#)) score.
- Clinical status, using the 11-point WHO Clinical Progression Scale (highest category that applies) ([Appendix 13](#)).
- Administration of dexamethasone base will be continued at 6 mg/day PO/IV (equivalent to 7.2 mg dexamethasone phosphate) up to a total cumulative dose of 60 mg, per physician judgement based on patient clinical condition and evolution.

7.4.2.4. Day 15

The following assessments will be performed on Day 15 (± 1), in remote or on-site visit:

- Concomitant medications.
- Adverse events/TEAEs.
- Functional status, using the Barthel index ([Appendix 7](#)) score.
- Clinical status, using the 11-point WHO Clinical Progression Scale (highest category that applies) ([Appendix 13](#)).

7.4.3. End of Study

End of study visit: all subjects will undergo safety and efficacy follow-up assessments on the protocol-specified Day 31 (± 3 days), earlier if patient withdraw from study or when treatment-related adverse events, treatment-emergent adverse events of special interest, and SAEs will be resolved/stabilised.

7.4.4. Study Schedule

A schedule of study assessments is provided in [Appendix 5](#).

8. SAMPLE SIZE AND DATA ANALYSES

A general description of the statistical methods to be used to analyse safety and efficacy data is outlined below. Specific details will be provided in the statistical analysis plan (SAP).

8.1. Determination of Sample Size

This is a multicentre, open-label, controlled Phase 3 study in which adults requiring hospital admission and O₂ supplementation for management of moderate COVID-19 infection will be randomised 1:1:1 to:

- Plitidepsin 1.5 mg arm: Patients will receive plitidepsin 1.5 mg/day IV in addition to dexamethasone on Days 1 to 3 ([See Section 5. Study treatments](#));
- Plitidepsin 2.5 mg arm: Patients will receive plitidepsin 2.5 mg/day IV in addition to dexamethasone on Days 1 to 3 ([See Section 5. Study treatments](#));
- Control arm: Patients will receive dexamethasone on Days 1 to 3. Additionally, in accordance with local treatment guidelines, patients in this group may receive a regulatory-approved antiviral treatment ([See Section 5. Study treatments](#)).

In case of patients in both plitidepsin arms, dexamethasone in Days 1 to 3 is administered as a premedication. The study allows up to a total cumulative dose of 60 mg of dexamethasone base (calculation of the total dose will also include corticosteroids administered within 72 hours before the start of the study treatment and dexamethasone administered as premedication).

Randomisation will be stratified for 3 factors:

- a) Geographical Region (Europe *versus* Rest of the World);
- b) Charlson Comorbidity Index (0-1 *versus* >1) ([Appendix 11 - Age-adjusted Charlson Index](#)); and
- c) Barthel Index (≥ 90 *versus* <90) ([Appendix 7 - Barthel Index for Functional Assessment](#))

From treatment initiation, patients will be followed in the hospital for at least 4 days and then through Day 31 (± 3 days) or resolution/stabilisation of treatment-related adverse events, treatment emergent adverse events of special interest and SAEs that occurred through Day 31.

A total sample size of 609 patients (203 in each arm) with 530 events necessary for the analysis of the primary endpoint has been calculated based on assumptions of a 1-sided type I error of 1.25% ($\alpha=0.0125$) with at least 80% power ($\beta=0.2$) to detect target hazard ratio (HR) of 1.4 in the time to sustained withdrawal of supplementary oxygen, which means a decrease in the median time to the event from 8 days⁴⁸ (control arm) to 5.7 days (plitidepsin). This sample size is adjusted for the multiple comparisons of each plitidepsin arm with control group by a Bonferroni adjustment. At the final analysis, if the HR is 1.27 or greater, in favour of any plitidepsin arm (equivalent to a decrease in the median time to sustained withdrawal of supplementary oxygen of 1.7 days or greater), then it is expected that the null hypothesis (i.e., $HR \leq 1$) will be rejected.

A futility analysis for efficacy/safety will be performed when 33% of events (sustained withdrawal of supplementary oxygen) have been reached. The rho family of beta-spending functions ($\rho=1.18$) will be used for the calculation of the stopping boundaries for futility in order to control type II error. The stopping boundaries for the futility analysis will be calculated with the actual number of events available in the ITT population at that moment; if the number of

events at the futility analysis is 116 in a pair comparison, the beta-spending corrected p-value to reject the alternative hypothesis should be higher or equal than 0.4199 and this p-value is associated with a $HR \leq 1.0382$.

If the recommendation of the IDMC is to discontinue one of the plitidepsin dosing arms at this futility analysis following the stopping rules, the study will continue from that point on a 1:1 randomisation fashion until the completion of the remaining treatment arms (203 patients per arm and 353 events of sustained withdrawal of supplementary oxygen in total necessary to perform the final analysis). The patients still ongoing in the dropped arm would continue to be followed up as per protocol.

8.2. Analysis Populations

Analysis of the primary and other time-to-event efficacy endpoints will be performed in the ITT population. Other secondary efficacy endpoints will be based on the FAS population. Supportive analyses will be performed on the Per Protocol population. A sensitivity analysis will be performed for the primary endpoint and other time-to-event efficacy endpoints in the FAS population, Safety endpoints analyses will be based on the Safety population.

8.2.1. Intent-to-Treat (ITT) Population

All patients randomised in the trial, regardless of whether they received treatment.

8.2.2. Full Analysis Set (FAS) Population

All randomised patients who have taken at least 1 dose of study treatment (plitidepsin or control) and with at least 1 postbaseline clinical status collected. FAS population will be analysed according to their randomised treatment.

8.2.3. Per Protocol Population

A subgroup of the FAS population that includes all patients who do not have any important protocol deviations that would interfere with the collection or interpretation of the efficacy data. Important protocol deviations will be defined in the SAP. Per Protocol population will be analysed according to their randomised treatment. Supportive efficacy analyses will be performed on this population.

8.2.4. As Treated Population

All patients who received any exposure to study treatment (plitidepsin or control). As Treated population will be analysed according to the treatment they actually received.

8.3. General Considerations

Demographic and baseline disease characteristic data will be summarised descriptively.

All summary tables for quantitative parameters will display n, mean, standard deviation, median, interquartile range (25th and 75th percentiles), and range (minimum and maximum). All summary tables for qualitative parameters will display counts and percentages.

The use of imputation methods in visits of patients with missing values will be detailed in the SAP.

8.4. Study Treatment Exposure

The study treatment exposure will be assessed by study treatment (plitidepsin, dexamethasone, and any regulatory-approved antiviral treatment, such as remdesivir or favipiravir) as the duration of treatment exposure during the study. The duration of study treatment exposure will be calculated by study treatment as: (date of the last study treatment taken – date of the first study treatment taken) + 1.

8.5. Efficacy Analysis

Analysis of the primary, key secondary and other time to event endpoints will be performed in the ITT population, and other secondary efficacy endpoints will be based on the FAS population. A sensitivity analysis will be performed for the primary endpoint and other time-to-event efficacy endpoints in the FAS population. Safety endpoints analyses will be based on the Safety population. Supportive analyses will be performed on the Per Protocol population.

8.5.1. Primary Efficacy Outcome Measures

Time-to event data (time to sustained withdrawal of oxygen supplementation) will be analysed using the Kaplan Meier method and presented with 95% CIs. A Cox regression model, including the levels of the randomisation stratification factors as covariates, will be applied to compare results between each dose of plitidepsin *versus* control arm. Hazard ratios, 2-sided 95% CIs, and p values for the comparison of each dose of plitidepsin *versus* control arm will be presented. The time-to-event between each dose of plitidepsin *versus* control arm will be compared using a 2-sided stratified log-rank test. The model will be adjusted for the randomisation stratification factors, i.e., Geographical Region (Europe *versus* Rest of the World), Charlson Comorbidity Index (0-1 *versus* >1) ([Appendix 11- Age-adjusted Charlson Index](#)) and Barthel index (≥ 90 *versus* <90) ([Appendix 7 – Barthel Index for Functional Assessment](#)). An unstratified log-rank test and Cox regression model will also be analysed as a sensitivity analyses. For both stratified and unstratified models, the hazard ratios, 2-sided 95% CIs, and p-values for the comparison of each dose of plitidepsin *versus* control arm will be presented. Proportional hazard assumption will be checked by means of a Cox regression including treatment and its interaction with time.⁴⁹ In case of strong rejection of proportionality, then restricted mean survival estimates and weighted log-rank tests (if applicable) will also be calculated in a sensitivity analysis in addition to HR.⁵⁰ The main analysis will be adjusted for multiplicity using the Hochberg step-up procedure to preserve the type I error rate in the comparison of each dose of plitidepsin *versus* control arm. If the accrual in any of the experimental arms is stopped after the interim futility analysis, the final analysis for the primary endpoint in the remaining arms will be performed at the 1.25% level using a Bonferroni-adjusted type I error rate.

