A total sample size of 609 patients (203 in each arm) with 530 events necessary for the analysis of the primary endpoint has been calculated based on a one-sided type I error rate of 1.25% (α -0.0125) with at least 80% power ($\beta=0.2$) to detect a target hazard ratio (HR) of 1.4 in the time to sustained withdrawal of supplementary oxygen, which means a decrease in the median time to the event from 8 days (control arm) to 5.7 days (plitidepsin). The sample size is adjusted for the multiple comparisons of each plitidepsin group with control group by a Bonferroni adjustment, although other advanced methods for correction of multiplicity will be used for the main analysis that will increase the power of the tests (<https://www.fda.gov/media/102657/download>). At the final analysis, if the HR is 1.27 or greater, in favour of any plitidepsin arm (equivalent to a decrease in the median time to sustained withdrawal of supplementary oxygen of 1.7 days or greater), then it is expected that the null hypothesis (i.e., $HR \leq 1$) will be rejected.

A futility analysis for efficacy/safety will be performed when 33% of events (sustained withdrawal of supplementary oxygen) have been reached. The rho family of beta-spending functions (with $\rho=1.18$) will be used for the calculation of the stopping boundaries for futility in order to control type II error. The stopping boundaries for the futility analysis will be calculated with the actual

number of events available in the Intent-To-Treat (ITT) population at that moment; if the number of events at the futility analysis is 116 in a pair comparison, the beta-spending corrected p-value to reject the alternative hypothesis should be higher or equal than 0.4199 and this p-value is associated with a $HR \leq 1.0382$.

If the recommendation of the IDMC is to discontinue one of the plitidepsin dosing arms at this futility analysis following the stopping rules, the study will continue from that point on a 1:1 randomisation fashion until the completion of the remaining treatment arms (203 patients per arm and 353 events of sustained withdrawal of supplementary oxygen in total necessary to perform the final analysis). The patients still ongoing in the dropped arm would continue to be followed up as per protocol and a Bonferroni-adjusted type I error rate of 1.25% will be kept for the comparison of the primary endpoint between the remaining plitidepsin arm and the control arm.

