4.5. Stopping Rules

The study will consist of approximately 609 patients included in the ITT population and randomised as 1:1:1 to 3 arms (plitidepsin 1.5 mg, plitidepsin 2.5 mg, and control) with 203 patients in each arm. A futility analysis for efficacy/safety will be performed when 33% of events (sustained withdrawal of supplementary oxygen) have been reached. The rho family of beta-spending functions (with $\rho=1.18$) will be used for the calculation of the stopping boundaries for futility in order to control type II error. The stopping boundaries for the futility analysis will be calculated with the actual number of events available in the ITT population at that moment; if the number of events at the futility analysis is 116 in a pair comparison, the beta-spending corrected p-value to reject the alternative hypothesis should be higher or equal than 0.4199 and this p-value is associated with a $HR \leq 1.0382$.

If the recommendation of the IDMC is to discontinue one of the plitidepsin dosing arms at this futility analysis following the stopping rules, the study will continue from that point on a 1:1 randomisation fashion until the completion of the remaining treatment arms (203 patients per arm and 353 events of sustained withdrawal of supplementary oxygen in total necessary to perform the final analysis). The patients still ongoing in the dropped arm would continue to be followed up as per protocol.

Study Termination

The sponsor reserves the right to close a study site or terminate the study at any time for any reason at the sole discretion of the sponsor. Study sites will be closed upon study completion. A study site is considered closed when all required documents and study supplies have been collected and a study site closure visit has been performed. Reasons for study termination may include, but are not limited to:

- Adverse events unknown to date (i.e., not previously reported in any similar investigational study drug trial with respect to their nature, severity, and/or duration).
- Increased frequency and/or severity and/or duration of known, anticipated, or previously reported AEs (this may also apply to AEs defined at enrolment as baseline signs and symptoms).
- Medical or ethical reasons affecting the continued performance of the study.
- Difficulties in the recruitment of patients.
- Cancellation of drug development.

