8.5.2. Key Secondary Efficacy Outcome Measures

Time-to event data will be analysed using the Kaplan-Meier method and presented with 95% CIs. A Cox-regression model, including the levels of the randomisation stratification factors as covariates, will be applied to compare results between each dose of plitidepsin *versus* control arm. Hazard ratios, 2-sided 95% CIs, and p-values for the comparison of each dose of plitidepsin *versus* control arm will be presented.

In the event that the primary endpoint is significant for both doses, the Hochberg procedure will be used to test the key secondary efficacy endpoints at the overall (2-sided) significance level of 0.05. This adjustment will not apply if the accrual in any of the experimental arms is stopped after the interim futility analysis. Details will be provided in the SAP.

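### Section 8.5.1 sets a 2-sided log-rank test beside an unlabelled 1.25% level for the arm-dropped analysis, although the design defines 1.25% as one-sided

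*Protocol*

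**What the plan says.** The design is one-sided. Section 8.1 bases the sample size on "a 1-sided type I error of 1.25" percent per comparison, and the synopsis has "a one-sided type I error rate of 1.25" percent. The null hypothesis is HR at or below 1, and rejection is expected at an observed HR of 1.27 or more.

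Section 8.5.1 governs the primary analysis. Each dose and control "will be compared using a 2-sided stratified log-rank test", with 2-sided 95% CIs. Hochberg is applied to the two doses, with no overall level or side printed. If accrual to an arm stops after the futility look, the final analysis "in the remaining arms will be performed at the 1.25% level", again with no side.

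Section 8.5.2 gives a level with a side, "at the overall (2-sided) significance level of 0.05", but for the key secondary endpoint and only when both doses succeed on the primary.

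For futility at 116 events in a pair, section 4.5 says the p-value "should be higher or equal than 0.4199" and ties this to HR at or below 1.0382. The synopsis and sections 3.1.1 and 8.1 agree. Section 8.9 prints 0.4993 beside the same HR. None of these places says whether the p-value is one- or two-sided.

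**The concern.** Within one paragraph, 8.5.1 tells the analyst to produce a 2-sided p-value and then names 1.25% as the level for the arm-dropped case. The direct way to carry that out is to compare the one with the other. The level was derived for a one-sided test, so this halves the error rate in the direction of benefit from 1.25% to 0.625%.

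At stake is the primary conclusion for the remaining dose: a band of observed results counts as success under 8.1 and as failure under 8.5.1. In an open-label trial that choice should not be left until the data can be seen.

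The futility p-value has a related labelling gap. The boundary is to be recalculated for the actual event count, so at any count other than 116 the printed HR no longer shows how the p-value is to be read.

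**Working it through.** **Inputs from the protocol.** Target HR 1.4; 1:1 within a pair; 353 events in the pair when one arm is dropped; control median 8 days; futility look at 116 pair events; rho = 1.18; total type II error 0.2; futility p 0.4199 (0.4993 in 8.9) with HR 1.0382.

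**Formulas** (normal approximation to the log-rank test, equal allocation, D events):
- critical HR = exp(2z/√D)
- fixed-design power = Φ(ln(1.4)·√D/2 − z)
- power with the futility look = P(Z₁ > z_fut and Z₂ > z), bivariate normal with means ln(1.4)·√116/2 = 1.812 and ln(1.4)·√353/2 = 3.161, and correlation √(116/353) = 0.573

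**1. Reproducing the design, one-sided 1.25% (z = 2.2414).**
- Critical HR = exp(2 × 2.2414/√353) = 1.2695; the protocol states 1.27.
- Median gain = 8 − 8/1.2695 = 1.7 days, as stated.
- Power = Φ(3.161 − 2.241) = 82.1% fixed, and 80.0% with the futility look; the protocol states at least 80%.
- 353 × 1.5 = 529.5, the stated 530 events over three arms.

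**2. Literal reading of 8.5.1: 2-sided p against 1.25% (z = 2.4977).**
- Critical HR = exp(2 × 2.4977/√353) = 1.305; median gain 8 − 8/1.305 = about 1.9 days.
- Power = Φ(3.161 − 2.498) = 74.6% fixed, and 73.1% with the (one-sided) futility look.
- Loss with the look: 80.0 − 73.1 = 6.9 percentage points.

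**3. Consistent reading: 2-sided p against 2.5%.** z is again 2.2414, so the critical HR is 1.2695 and power is 82.1% fixed and 80.0% with the look. Nothing changes from step 1.

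**4. Confidence interval.** A 2-sided 95% CI excludes 1 from exp(2 × 1.96/√353) = 1.232. Where a single dose must pass at one-sided 1.25%, observed HRs from 1.232 to just under 1.27 give an interval above 1 beside a failed test. A 97.5% two-sided CI uses z = 2.2414 and agrees with the test.

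**5. Futility p-value at 116 events.**

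| p | HR if one-sided | HR if two-sided (benefit side) |
|---|---|---|
| 0.4199 | exp(2 × 0.2021/√116) = 1.0383 | exp(2 × 0.8066/√116) = 1.162 |
| 0.4993 (8.9) | 1.0003 | 1.134 |

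The beta-spending rule confirms the one-sided reading. Beta spent is 0.2 × (116/353)^1.18 = 0.0538, which gives z = 0.203, p = 0.4196 and HR 1.0384, close to the printed 0.4199 and 1.0382. The 0.4993 fits the printed HR on neither reading.

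**The case against.** The strongest reply is that the intent is already visible. The synopsis and 8.1 define 1.25% as one-sided, give a directional null and print the HR 1.27 threshold. For the arm-dropped case, the synopsis and sections 3.1.1 and 8.9 say the 1.25% rate is kept, which points back to that definition. Nothing redefines 1.25% as two-sided. A 2-sided log-rank test judged at 2.5% is the same test as one-sided 1.25%. All of this stands, and it shows which reading was meant. But 8.5.1 does not say it, and a reader following that section alone gets a different threshold.

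Three stronger readings are tempting and are not supported:

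- **That the primary analysis as a whole is twice as strict as designed.** Section 8.5.1 attaches 1.25% only to the case of a dropped arm. With both arms continuing, Hochberg applies; at 2-sided 0.05 overall (assumed here from 8.5.2) no power is lost. That the primary Hochberg level is not printed is not a finding in itself, since such detail may be left to the SAP.
- **That the futility boundary moves to HR 1.16.** On that reading an arm with true HR 1.4 would be stopped in 15.7% of trials instead of 5.4%. But the 2-sided wording in 8.5.1 concerns the primary comparison, no section declares a 2-sided futility p-value, and HR 1.0382 is printed beside it each time. These figures describe a misreading, not the plan.
- **That the 95% CIs are wrong throughout.** They move no threshold and cost no power. Under Hochberg, when both doses have 2-sided p at or below 0.05 in favour of plitidepsin, both succeed and the 95% CI agrees with the decision. The mismatch arises only where one dose must pass at the 1.25% level.

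**Conclusion.** The contradiction is real but limited. In the arm-dropped case, 8.5.1 read literally raises the critical HR from 1.27 to 1.305 and lowers power at HR 1.4 from 80% to 73%, counting the futility look. Observed HRs in between pass under 8.1 and fail under 8.5.1. On the consistent reading the loss is zero.

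The figures assume proportional hazards, equal allocation, exactly 353 and 116 pair events, and the normal approximation without stratification. They are for one dose against control, not conditioned on the other dose having been dropped.

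The futility p-value needs a label. The definite error there is the 0.4993 in 8.9, which one-sided corresponds to HR 1.000, not 1.0382. Because the level sets a primary decision threshold and the correction costs almost nothing, it should be made.

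**What to change.** - **Section 8.5.1:** give the single-dose level as 1.25% one-sided (2.5% two-sided). State the Hochberg overall level as one-sided 2.5% (two-sided 5%). Add a 97.5% two-sided CI for the HR wherever the 1.25% level decides. Carry the same label to the other places that mention the arm-dropped level (synopsis, 3.1.1, 8.9).
- **Synopsis and sections 3.1.1, 4.5, 8.1 and 8.9:** label the futility p-value as one-sided in the direction of benefit, so that a boundary recalculated at another event count is read the same way.
- **Section 8.9:** replace 0.4993 so that it agrees with the 0.4199 printed elsewhere for HR 1.0382.

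No patients, events or procedures are added. The only downside is a slightly wider reported interval in the single-dose case.
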